**Appendix Table 8. Predicted HIV Incidencea Using Rectal Gonorrhea Incidence as the Determinant** 

Rectal Gonorrhea incidence (per 100 PY)	Predicted HIV Incidence Including 95% Prediction Interval (per 100 PY)
15	5.1 (2.51, 7.78)
20	6.3 (3.59, 8.91)
21	6.5 (3.80, 9.15)
22	6.7 (4.01, 9.38)
23	6.9 (4.21, 9.62)
24	7.1 (4.41, 9.86)
25	7.4 (4.62, 10.11)
30	8.5 (5.59, 11.34)
35	9.6 (6.63, 12.63)

a. Predictive model based on HIV and rectal gonorrhea regression analysis from 8 studies

Appendix Figure 4 below gives the power under different rectal gonorrhea rates and HIV infection rates. The power is calculated using the closed form power formula for the Poisson distribution, ie. not based on simulations.

# Appendix Figure 4. Power for Superiority Test against Historical Placebo

Assuming 4250 PY follow up per arm (based on estimated follow up time by the time of the primary analysis).

# Appendix 9 Assessment of Adherence and Efficacy Based on Dried Blood Spot Concentration

#### DBS 1.1 Background

Drug exposure level has been identified as the key factor in optimizing efficacy of HIV-1 PrEP. Although drug exposure level is related to multiple factors, adherence to drug (consistent drug administration) is the most important factor.

Two substudies will be conducted:

- 1) Cohort substudy to estimate the overall rate of adherence
- 2) Case-Control substudy to assess the association of adherence with efficacy in the GS-US-412-2055 study

The GS-US-412-2055 study is a randomized double-blind comparison of the safety and efficacy of F/TAF versus F/TDF administered once daily (QD) for at least 96 weeks in HIV-1 negative adults to show noninferiority of F/TAF to F/TDF with respect to prevention of HIV-1 infection. The study is being conducted in 94 sites across 11 countries in both North America and Europe. Enrollment for the GS-US-412-2055 study began in September 2016 and ended in June 2017. The primary endpoint will be assessed when all subjects have a minimum follow-up of 48 weeks and at least 50% of the subjects have 96 weeks of follow-up after randomization or permanently discontinued from the study.

Cards with dried blood samples (DBS) should be placed in a freezer within 1 day after blood draw and should be stored frozen for optimal stability. Samples put in a freezer later than one day after blood has been drawn or those with missing date for placement in the freezer will not be considered for these substudies and will not be sent to the analytical laboratory.

#### DBS 1.2 Exposure and Adherence

For these substudies, exposure is defined as tenofovir diphosphate (TFV-DP) concentration inside the red blood cells for each study drug group (F/TAF and F/TDF) as assessed by the dried blood spot (DBS concentration). Concentrations of TFV-DP in DBS assessments reflect cumulative exposure to study drug prior to the sampling time, and are not reflective of only the most recent daily dosing. Thus, as DBS concentration reflects long term exposure to study drug, it serves as an objective measure of overall or long-term adherence to study drug which is less affected by potential variability in daily drug administration (ie, missing a dose or doses, varying the time of day of drug administration).

TFV-DP concentrations are continuous measures and have been reported in units of femtomoles per punch (fmol/punch) or femtomoles per million viably cryopreserved peripheral blood mononuclear cells (f/M vPBMC). Previous work on DBS concentrations with F/TDF have been validated based on 3 mm punched disks.

Statistical Analysis Plan – End of Blinded Treatment Phase Analysis

Previous analyses {Anderson 2012a} of data from directly observed therapy (DOT) study (STRAND) in healthy volunteers along with the data from the iPrEX study have shown that F/TDF PrEP efficacy is associated with TFV-DP and that optimal efficacy may be achieved with concentrations consistent with ≥4 doses/week (see Appendix Table 9).

Appendix Table 9. TFV-DP Concentrations after DOT Dosing of F/TDF (STRAND Study) and Associated Risk Reduction and Proportion of Subjects Attaining TFV-DP EC90 in the iPrEx Study

	STRAND Study		iPr	EX	
Regimen	Concentra	tion (fmol/M vPBMC)		HIV-1 Acquisition	Subjects Attaining
(Doses / Week)	25 Percentile	Median	75 Percentile	Risk Reduction	TFV-DP EC90
2	6	11	13	76%	14%
4	25	32	39	96%	90%
7	31	42	47	99%	100%

Source: Emtricitabine tenofovir concentrations and pre exposure prophylaxis efficacy in men who have sex with men {Anderson 2012a}

A 72 week open-label cohort study {Grant 2014} of men and transgender women who have sex with men in previously enrolled PrEP trials (ATN 082, iPrEx, and US Safety Study) reported consistent results, Appendix Table 10.

Appendix Table 10. Estimated Dose and F/TDF PrEP Protection Associated with DBS Concentration

DBS Concentration (fmol/punch)	<llq< th="">LLQ-349	350-699	700-1249	≥1250	</llq<>	LLQ-349	350-699	700-1249	≥1250
Estimate dose (tablets/week)	None	<2	2–3	4–6	7
Follow-up (% of visits)	25%	26%	12%	21%	12%
HIV-1 infections (n)	18	9	1	0	0
Person-years per infection	384	399	179	316	181
HIV-1 incidence (95% CI)	4.70 (2.99–7.76)	2.25 (1.19–4.79)	0.56 (0.00–2.50)	0.00 (0.00–0.61)	0.00 (0.00–1.06)

Source: Uptake of pre exposure prophylaxis, sexual practices, and HIV 1 incidence in men and transgender women who have sex with men: a cohort study {Grant 2014}.

A more recent pharmacokinetic study of TFV-DP in DBS using DOT dosing of F/TDF (at daily dosing of 33%, 67%, or 100%) {Anderson 2018} has also shown consistent results. The modeling of data from this study has shown that the fitted (estimated) median (25 and 75 percentiles) TFV-DP DBS concentrations in men, were 375 (316, 444), 774 (653, 917) and 1389 (1173, 1646) fmol/punch for 2, 4 and 7 doses per week respectively {Anderson 2018}.

Considering that F/TAF delivers a lower dose of tenofovir and that using a 3 mm punch disk to quantify the TFV-DP levels in RBC are approximately 1/8th the values established for F/TDF, two 7 mm punched disks (an increase of 10.89 folds in total sample disk area) are used to quantify TFV-DP DBS concentration for participants who receive F/TAF.

A separate cross-over pharmacokinetic study of TFV-DP in DBS based on DOT dosing of F/TAF (at daily dosing of 33%, 67%, or 100%) is currently ongoing. Available preliminary data from this ongoing study {Yager 2019} (CROI abstract and presentation), and the previous F/TDF DOT study {Anderson 2018}, are used to develop the adherence bands for F/TAF based on DBS concentration. The observed 25th percentile, median and 75 percentiles from these sources are presented in Appendix Table 11.

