Appendix Table 11. Reported Estimates of DBS Concentrations at Different DOT Dose Levels

Daily Dosing in DOT Study Treatment		Q1	Median	Q3
33%	F/TDF (fmol/Punch)	424	518	670
	F/TAF (fmol/Punches) - Abstract	613	663	741
	F/TAF (fmol/Punches) - Presentation	510	663	788
67%	F/TDF (fmol/Punch)	806	946	1174
	F/TAF (fmol/Punches) - Abstract	991	1351	1586
	F/TAF (fmol/Punches) - Presentation	1030	1422	1683
100%	F/TDF (fmol/Punch)	1315	1542	1796
	F/TAF (fmol/Punches) - Abstract	1526	1928	2559
	F/TAF (fmol/Punches) - Presentation	1909	2199	2518

Ref: For F/TDF: {Anderson 2018} and F/TAF: Abstract {Yager 2019} and presentation

As expected (relative to TDF dose in F/TDF and DBS disk size), a shift up in the distribution of reported TFV-DP concentrations for F/TAF, compared to F/TDF, in Appendix Table 11 is observed; ~30% based the Week 12 data (Period 1 of the cross over study) and ~35% based the Weeks 12 and 24 data (Period 1 and 2 of the cross over study) included in the analysis of the abstract and presentation respectively. The cutoffs for F/TAF adherence levels can be estimated by adjusting the established DBS concentration for F/TDF adherence levels associated with HIV protection (or risk of acquiring infection) reported by {Grant 2014}, see Appendix Table 10. The proposed cutoffs, by either using 30% increase based on Period 1 results (free of any potential impact of cross-over design) or assuming dose proportionality and relying on Q1 for the 33% and 67% dosing levels, are presented in Appendix Table 12.

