#### DBS 1.3.4. Statistical Analysis

Summary tables, similar to those for the main study, will characterize the Cohort substudy for enrollment by country and investigator, demographics and baseline characteristics, baseline HIV risk characteristics, and subject disposition.

Descriptive statistics (n, mean, standard deviation, median, quartiles, minimum and maximum) for DBS TFV-DP concentration levels will be provided by treatment group and visit.

Median (Q1, Q3) of DBS concentration across visit time (horizontal axis) overlaid by horizontal lines corresponding to adherence thresholds for each treatment group, will be generated by treatment group.

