## DBS 1.4.7. Statistical Analysis

Summary tables, similar to those for the main study, will characterize the cases' and controls' demographics and baseline characteristics, baseline HIV risk characteristics and subject disposition by treatment group.

Graphical and/or tabular descriptive statistics (n, mean, standard deviation, median, quartiles, minimum and maximum) for DBS drug concentration levels for both cases and controls in each treatment group will be provided. Conditional logistic regression model will be used to estimate the odds ratio (and its 95% confidence interval) assessing the association between infection status and the adherence levels based on DBS concentration at HIV diagnosis for cases and controls. The 3 level adherence (Appendix Table 12) will be dichotomized to estimate two odds ratios:

- 1) the odds of HIV infection when adherence is low compared to when adherence is not low
- 2) the odds of HIV infection when adherence is high compared to when adherence is not high

The primary analysis will be within each treatment group and will include DBS drug concentration levels, at the time of infection as the primary predictor. If a control subject has DBS collected at more than one visit within a window, then the record with DBS collection study day closest to the diagnosis study day of the case subject will be selected and if they are equally apart from the diagnosis study day of the case subject (one before and one after) then the one after the study day of the case subject will be selected.

DBS cards at the time of diagnosis may not have been collected for infected subjects or the sample may not meet specifications and be rejected by the analytical laboratory. In general, missing DBS concentration at the time of HIV diagnosis will be imputed by considering:

- 1) the last known TFV-DP concentration (C) prior to diagnosis
- 2) days between the last dose date and HIV diagnosis (HIV Dx date last dose date) where any negative days (last dose is after HIV Dx) are set to 0
- 3) days between the last TFV-DP concentration (C) prior to diagnosis and HIV diagnosis (HIV Dx date last DBS date)
- 4) the decay rate, k, of TFV-DP concentration in RBC calculated based on half-life,  $t_{1/2}$ , of each treatment group, where k  $0.693/t_{1/2}$ .

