TFV-DP has shown the median (range) half-life of 17 (14 to 23) days for F/TDF in previous DOT studies of F/TDF {Anderson 2018} and median (IQR) 20 days (18, 21) for F/TAF (preliminary data from Yager 2019 CROI presentation).

[figure not shown]
A sensitivity analysis will be conducted by setting the adherence level to "Low", for subjects suspected to have acquired HIV prior to first dose date of study drug. These are defined as subjects for whom HIV infection prior to first dose date of study drug cannot be excluded as the subjects did not have a Covance HIV antibody or HIV-1 RNA test analyzed between first dose date (inclusive) and prior to the date of diagnosis of HIV infection).

Stratified Wilcoxon test (stratified based on matching criteria) will test the difference between distribution of DBS concentrations (continuous measure) observed in cases and controls. The two-sided p-value from the stratified Wilcoxon test will be reported.

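### Dried-blood-spot readings at Weeks 4 and 12 count TFV-DP left over from pre-study F/TDF as study-drug adherence, in both arms but far more strongly in the F/TAF arm

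*SAP*

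**What the plan says.** **Who carries residual drug.** Protocol Section 4.3 bars only investigational HIV agents in the 30 days before screening. It requires no washout of marketed F/TDF. SAP Section 7.6.3 defines baseline F/TDF use by an end date from Screening to the first dose inclusive, and Protocol Section 6.2.2 allows up to 30 days between Screening and Day 1.

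**The assay.** On the F/TDF side, SAP Appendix 9 (DBS 1.2) states: "Previous work on DBS concentrations with F/TDF have been validated based on 3 mm punched disks". For the F/TAF arm, "two 7 mm punched disks (an increase of 10.89 folds in total sample disk area) are used to quantify TFV-DP DBS concentration". Appendix Table 12 sets Low/Medium/High at 350 and 700 fmol/punch for F/TDF, and at 450 and 900 fmol/punches for F/TAF.

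**Decay.** DBS 1.4.7 states "TFV-DP has shown the median (range) half-life of 17 (14 to 23) days for F/TDF in previous DOT studies of F/TDF" and uses first-order decay with k = 0.693 divided by the half-life.

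**The analyses.** In the cohort substudy (DBS 1.3.4), "Descriptive statistics (n, mean, standard deviation, median, quartiles, minimum and maximum) for DBS TFV-DP concentration levels will be provided by treatment group and visit", with median plots overlaid by the adherence thresholds. In the case-control substudy (DBS 1.4.7), "The primary analysis will be within each treatment group and will include DBS drug concentration levels, at the time of infection as the primary predictor". Controls are matched on arm, visit of diagnosis, rectal STI and location (DBS 1.4.5). SAP Section 1.2 has DBS sampling start at Week 4.

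**The concern.** TDF and TAF yield the same analyte, so the assay cannot tell old F/TDF from study drug. Appendix 9 nevertheless describes the DBS level as cumulative exposure to study drug. The F/TAF assay multiplies residual TDF-derived TFV-DP by the larger disk area, then reads it against bands set for the much lower red-cell levels that TAF produces.

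The SAP recognises carry-over elsewhere. When deriving the F/TAF cut-offs it can rely on Period 1 of the external crossover study because that period is "free of any potential impact of cross-over design". Section 3.3 adjusts BMD, renal, weight and BMI analyses for baseline F/TDF. The DBS analyses have no exclusion, matching, adjustment or stratified concentration summary for it.

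Both substudy objectives depend on DBS meaning study-drug adherence: the cohort characterises adherence in each arm, and the case-control study relates adherence to efficacy. A recent F/TDF user who stops taking study drug can be labelled High at Week 4, whether case or control. Recent users who do take study drug have their continuous concentrations raised. DBS 1.4.7 imputes a missing value at diagnosis from the last earlier concentration, so a contaminated Week 4 value could be carried on.

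**Working it through.** **Inputs, all from SAP Appendix 9.** Fitted F/TDF medians in men "were 375 (316, 444), 774 (653, 917) and 1389 (1173, 1646) fmol/punch for 2, 4 and 7 doses per week" (DBS 1.2). Observed median at 100% dosing 1542 fmol/punch (Appendix Table 11). Half-life 17 days, range 14 to 23 (DBS 1.4.7). Cut-offs from Appendix Table 12. Week 4 is Day 28, Week 12 is Day 84, Week 24 is Day 168 (SAP Table 3-1).

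**The plan's own figures.** Area ratio: 2 × (7/3)² = 10.89, as stated. Cut-offs: 350 × 1.3 = 455 and 700 × 1.3 = 910, rounded in the SAP to 450 and 900.

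**Does the reading scale with area?** The SAP says that on a 3 mm punch F/TAF "TFV-DP levels in RBC are approximately 1/8th the values established for F/TDF". Then 10.89/8 = 1.36, close to the 30 to 35% upward shift it reports for the larger disks. Linear scaling therefore agrees with the SAP.

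**Residual with no study drug taken.** F/TAF assay: C × 10.89 × 2^(−d/h). F/TDF assay: C × 2^(−d/h). Here C is the pre-study level, d the days since the last F/TDF dose, and h the half-life.

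F/TAF arm, F/TDF stopped at Day 1:

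| Prior F/TDF use | Visit | h = 14 | h = 17 | h = 23 |
|---|---|---|---|---|
| Daily (1389) | Week 4 | 3,781 High | 4,829 High | 6,505 High |
| Daily (1542) | Week 4 | 4,198 High | 5,361 High | 7,221 High |
| 4 doses/week (774) | Week 4 | 2,107 High | 2,691 High | 3,625 High |
| 2 doses/week (375) | Week 4 | 1,021 High | 1,304 High | 1,756 High |
| Daily (1389) | Week 12 | 236 Low | 492 Medium | 1,203 High |
| Daily (1542) | Week 12 | 262 Low | 547 Medium | 1,336 High |
| 4 doses/week (774) | Week 12 | 132 Low | 274 Low | 670 Medium |

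By Week 24 a daily user reads 16 to 18 at h = 17 (Low).

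**F/TDF stopped 30 days before Day 1 (d = 58 at Week 4), F/TAF arm.** At h = 17 a daily user reads 1,421 to 1,578, still High. At h = 14 the reading is 856 (Medium) from 1389 and 950 (High) from 1542. A prior user at 4 doses/week reads 792 at h = 17 (Medium).

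**How long it lasts.** Time to fall below 450 is h × log2(C × 10.89/450). At h = 17 this is 86 days from 1389 and 89 days from 1542. Medium on Day 84 therefore needs F/TDF to have stopped no more than about 2 to 5 days before Day 1. For 1542 the time runs from 73 to 120 days over h = 14 to 23.

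**F/TDF arm, same daily user, no study drug.** Week 4 at h = 17: 1389 × 0.319 = 443 and 1542 × 0.319 = 492, both Medium. At h = 14 the first is 347, just inside Low. Week 12: 45 to 50, Low.

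**Imbalance between arms.** Relative to each arm's High cut-off, the F/TAF reading is larger by 10.89 × 700/900 = 8.5 times.

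**The case against.** **Both arms are affected.** A reader might infer that carry-over acts in the F/TAF arm alone because the F/TDF arm keeps the 3 mm scale. The Medium readings of 443 and 492 contradict that, and a remedy confined to F/TAF would create a new imbalance.

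**Week 12 is fragile.** A reader might infer that recent F/TDF users generally read Medium at Week 12. The documents support this only for daily users who continue to about Day 1. Even then the outcome runs from Low to High across the quoted half-life range.

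**Reach is limited.** At most the first two DBS visits of a phase lasting at least 96 weeks are touched. The non-inferiority comparison (SAP Section 6.2.5) does not use DBS, and pill counts and self-report also measure adherence (Section 4.2.3). DBS 1.3.4 plots medians against thresholds rather than classifying participants, and medians move less than means.

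**Some handling exists.** The baseline risk tables for both substudies will show baseline F/TDF use. A sensitivity analysis in DBS 1.4.7 sets suspected pre-dose infections to Low. Neither addresses residual drug in uninfected participants.

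**The analysis may be closed.** SAP Section 8 says the PK analysis is done and will not be repeated, whereas Section 4.2.3 says DBS levels will be analysed.

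All of this narrows the point. None of it removes the Week 4 misreading. Nor does it help to argue that TFV-DP is exposure whatever its source: Appendix 7 puts protective PBMC levels at only about 10 days after stopping F/TDF, well short of Day 28.

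**Conclusion.** The concern holds for early visits. Week 4 is the firm part: for F/TDF stopped at Day 1, median prior users at 2, 4 and 7 doses/week all read High in the F/TAF arm without taking F/TAF, at every half-life in the quoted range. Week 12 is conditional, and Week 24 onwards is clear. The F/TDF arm is affected too, much less.

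This rests on readings scaling with disk area, on prior users being at the quoted steady-state levels, and on the SAP's half-life.

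The share of baseline F/TDF users and the spread of their stopping dates are not in the documents. A reader might multiply the Week 4 residual by a guessed share. Assuming 5 to 20% of the arm, 5,361 × 0.05 = 268 and 5,361 × 0.20 = 1,072 fmol would be added to the F/TAF mean. That is a ceiling, because it treats every baseline user as a median daily user with no gap. The effect on the cohort summaries and the odds ratios cannot be sized.

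A reader might also infer that the HIV comparison is biased. It is not: the fault lies in the supporting adherence evidence.

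**What to change.** - **DBS 1.3.4:** report concentrations by arm, visit and baseline F/TDF use (yes/no). In both arms, do not read samples taken before Week 24 from recent F/TDF users against the adherence thresholds.
- **DBS 1.4.7:** exclude Week 4 and Week 12 DBS records of recent F/TDF users, cases and controls in both arms, from the odds-ratio and stratified Wilcoxon analyses, or at least do so as a sensitivity analysis. Do not carry those values forward in the imputation.
- **Define recent use:** the Section 7.6.3 flag is the minimum. Earlier users identified under Section 7.6.2 can be added by end date. The longest clearance time above, 120 days, indicates how far back residual drug can matter.
- **What not to rely on:** subtracting the residual needs a Day 1 DBS level, and none is collected. Matching or adjustment alone leaves the early reading uninformative within the baseline-user stratum.
- **Reconcile Section 8 with Section 4.2.3.** If the DBS analysis has already been run, label the re-run as post hoc.

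The cost is SAP wording and a re-run on data already held, with the baseline flag already derived. The downside is fewer usable Week 4 and Week 12 DBS records.

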Appendix Table 11. Reported Estimates of DBS Concentrations at Different DOT Dose Levels

Daily Dosing in DOT Study Treatment		Q1	Median	Q3
33%	F/TDF (fmol/Punch)	424	518	670
	F/TAF (fmol/Punches) - Abstract	613	663	741
	F/TAF (fmol/Punches) - Presentation	510	663	788
67%	F/TDF (fmol/Punch)	806	946	1174
	F/TAF (fmol/Punches) - Abstract	991	1351	1586
	F/TAF (fmol/Punches) - Presentation	1030	1422	1683
100%	F/TDF (fmol/Punch)	1315	1542	1796
	F/TAF (fmol/Punches) - Abstract	1526	1928	2559
	F/TAF (fmol/Punches) - Presentation	1909	2199	2518

Ref: For F/TDF: {Anderson 2018} and F/TAF: Abstract {Yager 2019} and presentation

As expected (relative to TDF dose in F/TDF and DBS disk size), a shift up in the distribution of reported TFV-DP concentrations for F/TAF, compared to F/TDF, in Appendix Table 11 is observed; ~30% based the Week 12 data (Period 1 of the cross over study) and ~35% based the Weeks 12 and 24 data (Period 1 and 2 of the cross over study) included in the analysis of the abstract and presentation respectively. The cutoffs for F/TAF adherence levels can be estimated by adjusting the established DBS concentration for F/TDF adherence levels associated with HIV protection (or risk of acquiring infection) reported by {Grant 2014}, see Appendix Table 10. The proposed cutoffs, by either using 30% increase based on Period 1 results (free of any potential impact of cross-over design) or assuming dose proportionality and relying on Q1 for the 33% and 67% dosing levels, are presented in Appendix Table 12.

## Appendix Table 12. Adherence Level Definitions Based on DBS Concentration

	Adherence Level (Daily Tablets/Week)		
	Low (<2)	Medium (2-3)	High (≥4)
F/TDF (fmol/Punch)	< 350	350 to < 700	≥ 700
F/TAF (fmol/Punches)	< 450	450 to < 900	≥ 900

These cutoffs for F/TAF may change or additional sensitivity analysis may be conducted if the updated data from the ongoing DOT study of F/TAF or the analysis of adherence bands associated with TFV-DP concentrations (fitted results) are completed and are available to Gilead.

#### DBS 1.3 The Cohort Substudy

#### DBS 1.3.1 Study Design

In order to estimate the rate of adherence based on the DBS concentration, a cohort of approximately 10% of the subjects who were randomized in Study GS-US-412-2055 were randomly pre-selected. The subjects were selected early during study conduct (December 2016) based on the planned subject number ranges for the study (starting with 2000). The selection for the Cohort substudy, randomly selected 1 out of every 10 subject numbers expected to be used for enrollment (Section 1.2, Pharmacokinetics).

